## **2.5.6 Withdrawal from the Study due to Non-adherence to Treatment**

Non-adherence to the study of treatment with clopidogrel, alternative antiplatelet or other prescribed medication or a patient's decision to avoid or discontinue study procedures is grounds for withdrawal from the study due to non-adherence.

Evaluations for medication non-adherence should be performed at each study-planned follow-up visit using the Brief Medication Use Questionnaire (BMQ) [26].

No single (so-called "gold standard") tool is presented for assessing non-adherence to medication treatment. The highly specific and sensitive BMQ, currently being developed, was selected for the assessment of non-adherence to treatment. Based on characteristics of drug consumption by evaluating (scaling) the responses to nine simple questions and amounts of medication taken "during the past week" and the patient's opinion on the effects, adherence to medication treatment can be calculated. Assessments carried out during the observation period will reveal possible barriers that lead to non-adherence. The results of the assessment of the medication regimen, trust in treatment, and attitude determine the state of repeated or sporadic non-adherence or adherence. To influence the identified factors of non-adherence, the patient will be consulted during the observation period, and it will be possible to overcome sporadic non-adherence cases.

In the event of repeated non-adherence, procedures for withdrawing the patient from the study will be considered.

These procedures include:

- Informing the patient about his/her withdrawal from the study;
- Justification of the decision to withdraw the patient from the study;
- Conducting follow-up assessments of clinical outcomes;
- Clinical examinations are conducted to assess the patient's current condition and safety;

In cases where a patient is withdrawn from the study due to non-adherence to medication treatment during the 3rd, and 6th month of follow-up, a new study subject may be included in the study in his/her place, with allocation to the appropriate experimental or control group. After the 6-month follow-up period, a patient withdrawn from the study should not be replaced by a new study subject.

Withdrawal from the study will be reviewed by the study center investigator, principal investigator, and data management team. The patient will be informed of the non-adherence case and the decision to withdraw from the study.

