Hypothesis	
The research question is how antiplatelet treatment for preventing major adverse cardiovascular events after ePCI works in chronic coronary artery disease when guided by personal genetic characteristics for drug metabolism.
 
The study aims to test two research hypotheses:
 
 
• CYP2C19 genotype-guided clopidogrel treatment ensures better clinical outcomes when compared with conventional treatment selection led without CYP2C19 genotyping.
 
• CYP2C19 genotype-guided antiplatelet treatment could be beneficially applied in real-world clinical practice.
 

Design	Multicenter, randomized, parallel-group controlled study

Primary Objectives	
The aim of the study is to evaluate CYP2C19 allele genotype-guided antiplatelet treatment outcomes.
 
The specific objectives of the study are:
 
 
— Pre-assignment and randomization of study participants into study arms for conventional and CYP2C19 genotype-guided antiplatelet treatment with clopidogrel or an alternative P2Y12 inhibitor;
 
— providing RT-PCR-based pre-, analytical and post-analytical processes of the study to ensure CYP2C19 *2, *3 allele profiling for detection of study participants with normal functioning (NFA) and loss of function (LOF) allele;
 
— Observation of clinical outcomes of patients in the study groups during the 12 months of treatment;
 
— Evaluation of processes and non-clinical outcomes of clinical case management;
 

Secondary Objectives	
 
— Implementation of the methods and procedures provided by the research protocol into a real clinical practice pipeline;
 
— Raising awareness and understanding of the role of laboratory services by bridging clinical, laboratory practice professionals and other stakeholders to achieve patient-centeredness and improve clinical outcomes;
 
— Evaluation of clinical practice models based on assessments of molecular markers;
 
— Disseminate study results through publishing a scientific paper in a peer-reviewed journal and abstracts for reporting study results.
 

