Concomitant use of other drugs that inhibit CYP3A4 or CYP2C19 with clopidogrel may reduce the expected positive effects of treatment and induce negative ones, since the hepatic metabolism of clopidogrel is also mainly mediated by CYP2C19 and to a lesser extent by CYP3A4. The concomitant use of drugs that inhibit CYP3A4 or CYP2C19 can be assessed by reviewing the patient's medical history. Their use is prohibited during the study and must be discontinued 2 weeks before enrollment, otherwise, it will constitute an exclusion criterion from the study. Below is a list of drugs that inhibit CYP3A4 or CYP2C19 and their use is prohibited during the study period. If the use of these medications is necessary, the patient will be considered for withdrawal from the study.

— CYP3A4 inhibitors:

Omeprazole, clarithromycin, erythromycin, diltiazem, itraconazole, ketoconazole, ritonavir, verapamil, grapefruit;

— CYP2C19 inhibitors:

Omeprazole, fluvoxamine, ticlopidine, efavirenz, chloramphenicol, fluoxetine, delavirdine, gemfibrozil, stiripentol, bortezomib.

The PPI of choice for patients included in the study is pantoprazole. However, according to the CPIC CYP2C19 genotype-based PPI dosing guidelines and recommendations [25], carriers of CYP2C19 \*2, \*3 LOF alleles are at increased plasma concentrations of this PPI and increased risk of toxicity with prolonged treatment (>12 weeks). Despite the expected increase in treatment efficacy, the drug dose should be reduced by 50% for use >12 weeks and continued monitoring for maintenance of efficacy.

BMI is determined by calculating the results of simple anthropometry.  $BMI \geq 40 \text{ kg/m}^2$  defines clinical obesity/fatty states. They are considered an independent risk factor for repeated MACCE in CAD cases. Prevention of this risk factor requires consistent, intensive measures of lifestyle changes (diet, physical activity) and drug treatment for at least 6-12 months, during which it is impossible to achieve results during the study inclusion and observation period. The excess of risks due to this factor during the study may be an important reason for the dispersion of the study effects. Including patients with this clinical characteristic in the study group, only with the drug treatment provided by the study, would be ethically unjustified. Accordingly,  $BMI \geq 40 \text{ kg/m}^2$  is an important exclusion criterion from the study.

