### **3.0 Risk Analysis**

#### **3.1 Expected Risks**

No specific health risks are associated with study activities or procedures for study participants. CYP2C19 \*2, \*3 genotyping with the RT-PCR-based allele discrimination method, applied on randomly selected patients in the experimental arm, belongs to the category of diagnostic procedures that do not involve health risks.

Investigational medicinal products used in the study also do not pose additional health risks to patients. Antiplatelet drugs selected for treatment interventions are real-world clinical practice drugs for the study participants' treatment in conditions with clinical characteristics of study interest. Current guidelines recommend routine use of these medications in post-PCI settings. The use of the investigational product, based on the results of CYP2C19 \*2, \*3 genotyping, is a patient-centered and precision treatment selection approach that increases the chances for prevention of MACCE. Thus, it represents a significant benefit to patients and cannot be considered a health risk determinant.

Non-adherence is a significant problem in the use of long-term antiplatelet treatment with P2Y12 inhibitors. As part of the clinical follow-up provided by the study investigators and healthcare team, patients included in the study will be assessed for adherence to treatment using the BMQ. The questionnaire will assess adherence not only to P2Y12 inhibitors but also to other medications used to reduce the risk of CAD in the patients included in the study. Accordingly, this study procedure will make it possible to identify and prevent non-adherence to drug treatment (sporadic or recurrent), which will significantly reduce the possibility of developing MACCE and thus be beneficial for the subjects included in the study.

The health risks for study participants are related to the development of the disease/condition under study, CAD, MACCE (cardiovascular death, nonfatal myocardial infarction, recurrent angina, repeat PCI, stent thrombosis, ischemic stroke, transient ischemic attack, intracerebral hemorrhagic stroke), and known, expected, adverse effects of drug treatment (intracerebral hemorrhage, GI bleeding, other bleeding, thrombotic thrombocytopenic purpura). However, these cannot be considered as health risks related to the study. Such adverse events may develop in real-world practice even outside of research interventions.

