## **3.3 Early Withdrawal of a Study Participant**

A study participant may withdraw from the study at any time during the study and for any reason, whether identifiable or not, by their own free will. This decision and the patient's independent choice are presented in the informed consent form.

A study participant may also be withdrawn early from the study if there is persistent non-adherence to the study follow-up and treatment procedures (see Chapter 2.5.6, Withdrawal from the Study Due to Non-Adherence to Treatment).

A study participant may be withdrawn early from the study based on a clearly stated justification by the investigator or the study sponsor if it is in the patient's best interests to discontinue the study.

The basic reasons for withdrawal from the study are considered as follows:

- If any abnormal study result, symptom, or measurement parameter is detected and resolution, improvement, correction or stabilization of which may require a long period of treatment and/or observation and will change the course of the study-defined follow-up and treatment;
- Any adverse event that may persist during the follow-up period, or require a change or discontinuation of the study-defined treatment, or disrupt the study-defined clinical evaluation plan, or be associated with a severe outcome.
- Any adverse event that may be masked by the use of different medical care regimens than those specified in the study protocol;
- If study treatment intervention, it may pose an expected AAME, a health threat, requiring discontinuation and modification. These conditions require modified treatment measures and regimens other than those specified in the study, including hospitalization. In addition, clinical conditions that may be characteristic of AAME may be exclusion criteria from the study.
- An adverse event related to treatment with P2Y12 inhibitors is a study endpoint, after which the study-planned follow-up is no longer required.
- The MACCE determines the study endpoint, and further measures are no longer required.

In these cases, study participants are discontinued from the study-planned follow-up; the necessary assessments of early withdrawal from the study should be conducted, and the reason for early withdrawal from the study should be determined (evaluated). In these cases, the patient continues to be monitored and treated by the medical support team.

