The investigator will describe and analyze the reason for the study participant's early withdrawal, which is part of the routine medical records. An adverse clinical event will be registered in the study data form.

The investigator will inform the study participant of the decision to withdraw from the study early and about further follow-up and treatment measures.

Patient data collected before withdrawal will be used for study purposes, with confidentiality, following the procedures provided and the terms presented to the patient in the informed consent form.

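### Withdrawal for repeated non-adherence or need for a listed inhibitor ends planned follow-up, so later deaths and other 12-month endpoints are not systematically collected and, under Appendix 3, count as non-events

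*Combined protocol and SAP*

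**What the plan says.** - **Non-adherence.** Section 2.5.6 lists "Non-adherence to the study of treatment with clopidogrel, alternative antiplatelet or other prescribed medication" as a ground for withdrawal from the study, not only from a drug. Sporadic cases are counselled; for the rest, "In the event of repeated non-adherence, procedures for withdrawing the patient from the study will be considered". Section 3.3 repeats the ground: "A study participant may also be withdrawn early from the study if there is persistent non-adherence to the study follow-up and treatment procedures".
- **Inhibitors.** After listing the CYP3A4 and CYP2C19 inhibitors, Section 2.4.4 states: "If the use of these medications is necessary, the patient will be considered for withdrawal from the study".
- **What withdrawal means.** The Synopsis (Follow-up) counts non-compliance as early withdrawal and provides one evaluation within 72 hours. Appendix 2 has a single withdrawal column. Section 3.3 says of withdrawn participants that "study participants are discontinued from the study-planned follow-up", and Section 3.4 accepts that their study period may be shorter than 12 months.
- **What is kept.** "Patient data collected before withdrawal will be used for study purposes" (Section 3.3). Section 2.4.2 treats some dropouts as a source of data.
- **Replacement.** Section 2.5.6 allows a non-adherent participant withdrawn up to the 6-month follow-up to be replaced by a new one.
- **Endpoints and counting.** The primary endpoints in Section 2.6.1 are all-cause and cardiovascular death within 12 months. Appendix 3 divides events by the total number of participants in each arm, and builds its hazard ratios from those proportions. Section 2.6.3 also names Cox regression. No analysis set is defined.
- **Aim.** The second hypothesis is that "genotype-guided antiplatelet treatment could be beneficially applied in real-world clinical practice".

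**The concern.** Adherence to the assigned drug is part of how a treatment strategy performs in routine care. Ending follow-up when adherence fails moves the question towards how the strategy performs while participants comply, which is not the second hypothesis.

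The loss is also unlikely to be neutral. Section 3.1 says adherence assessment will "identify and prevent non-adherence to drug treatment (sporadic or recurrent), which will significantly reduce the possibility of developing MACCE", so the plan itself links non-adherence to higher risk. A participant withdrawn at month 3 who dies at month 8 is a 12-month death that no scheduled procedure would find, yet that participant may remain in the denominator. Absolute benefit, which Appendix 3 reports for nearly every endpoint, would rest on understated risks. If the arms lose different shares, the ratio measures are distorted as well. Replacing non-adherent participants selects further for compliance.

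**Working it through.** The plan attaches no figure to these withdrawals. Its only related number is the 25% non-completion in Section 2.4.2: 0.25 × 240 = 60 participants, covering four reasons, with no share given for non-adherence. What follows illustrates the mechanism and is not a forecast.

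**Assumed inputs.** No drug effect. A 12-month risk of 10% while adherent (the upper end of the 1–10% that Section 3.2.1 gives for MACCE). Hazard doubled from month 3 in those who become non-adherent, all of whom are withdrawn at month 3. Share withdrawn *p* = 20% guided, 10% control.

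**Risks.**
- *h* = −ln(0.9) = 0.1054 per year.
- Full-year risk in a non-adherent participant: 1 − exp(−0.25*h* − 2 × 0.75*h*) = 0.1684.
- Part of that risk seen before withdrawal: 1 − exp(−0.25*h*) = 0.0260.

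**Arm risks.** Full follow-up is (1 − *p*) × 0.10 + *p* × 0.1684. The crude count over the whole arm is (1 − *p*) × 0.10 + *p* × 0.0260.

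| Withdrawn, guided v control | Full follow-up | RR | Crude count | RR |
|---|---|---|---|---|
| 20% v 10% | 11.4% v 10.7% | 1.06 | 8.5% v 9.3% | 0.92 |
| 15% v 10% | 11.0% v 10.7% | 1.03 | 8.9% v 9.3% | 0.96 |

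**Equal withdrawal.** The RR stays 1.00, but each arm's risk is understated by *p* × (0.1684 − 0.0260): 1.4 percentage points at *p* = 10% and 2.8 at *p* = 20%.

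**Rarer events, such as death.** As the base risk becomes small, the two RRs tend to (1 + 0.75 × 0.20)/(1 + 0.75 × 0.10) = 1.07 and (1 − 0.75 × 0.20)/(1 − 0.75 × 0.10) = 0.92, so the ratios hardly depend on the 10%.

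**Other ways of counting.** In this example the hazard is the same in both arms until withdrawal, so a Cox model censoring there gives 1.00. Dropping withdrawn participants altogether gives 10%/10% = 1.00. Neither recovers the 1.06 that full follow-up would show.

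**A second model: equal non-adherence, unequal use of discretion.** Assume 30% of each arm is non-adherent, an adherent risk of 8%, non-adherent risk *k* times that, and half of a withdrawn participant's risk unseen. True risk is 0.7 × 0.08 + 0.3 × 0.08*k*; the part missed is *p* × 0.08*k* × 0.5. With 30% guided and 15% control withdrawn and *k* = 2, this is (0.104 − 0.024)/(0.104 − 0.012) = 0.080/0.092 = 0.87 against a true RR of 1. For *k* = 1 and 3 it is 0.92 and 0.84. With the shares exchanged it is 1.09, 1.15 and 1.20 for *k* = 1, 2 and 3. The direction follows the arm that loses more.

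**The case against.** **Only compliant participants are assessed.** A reader might infer this from the rules. The documents do not support it. Sporadic non-adherers stay in, withdrawal for repeated non-adherence is only considered, outcomes are assessed at exit and earlier data are used. Withdrawal for any reason is itself an endpoint, and repeated non-adherence is an Appendix 3 indicator. What stands is narrower: nothing schedules endpoint or vital-status collection after exit. Section 2.5.6 does list a follow-up assessment of clinical outcomes, but as one of the steps of withdrawal.

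**The result would reverse.** The move from 1.06 to 0.92 might be read as a prediction. It is not. About 110 of the 160 guided participants take clopidogrel, as controls do. If they withdraw at the control rate of 10% (11 people), a guided rate of 20% (32 people) needs 21/50 = 42% of those on alternative drugs to be withdrawn; a guided rate of 15% (24 people) needs 13/50 = 26%. The first scenario withdraws 32 + 8 = 40 of 240 (16.7%), a large part of the 25% allowed for all reasons, and places every withdrawal at the first visit. It also needs the crude count. With 160 v 80 participants, an RR of 0.92 has a 95% interval of about 0.39 to 2.16, so the shift is well inside sampling error. This objection stands against any claim about size or direction.

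**Knowledge of the arm drives withdrawal.** Section 2.5.4 discloses results to participants and the care team. Section 2.5.6 gives the review to the site investigator, principal investigator and data management team, and Section 2.4.4 names no decision-maker. Differential withdrawal is possible but not shown. Nor do the documents show that inhibitor use would differ between arms, since the rule covers all of them, or that starting a listed drug is itself an outcome.

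**Conclusion.** The point holds in limited form. Repeated non-adherence or inhibitor need can end planned follow-up, and endpoints after the exit evaluation are then not systematically collected, although the primary endpoints run to 12 months and one hypothesis is about routine practice. Counted as Appendix 3 describes, absolute risks are understated even with equal withdrawal (1.4 to 2.8 points on the assumed inputs). The randomised comparison is biased if withdrawal differs, in either direction. The size cannot be fixed from the documents: the withdrawal shares, their timing and the excess risk are all assumed, and the plan does not say how withdrawn or replaced participants enter the denominators. The change should be made because it is cheap and removes the dependence on those unknowns, not because a particular bias has been demonstrated.

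**What to change.** 1. In Section 2.5.6, the inhibitor narrative of Section 2.4.4, the Synopsis withdrawal reasons and Section 3.3, state that non-adherence or inhibitor exposure is recorded and that the participant remains in the scheduled 3-, 6- and 12-month endpoint and vital-status follow-up unless consent is withdrawn. Changing only some of these places would leave the rule in force elsewhere.
2. Define the main analysis as all randomised participants in their randomised group. Any on-treatment analysis is supplementary, and the Appendix 3 non-adherence rows stay as descriptive outcomes.
3. State that any replacement under Section 2.5.6 is additional and does not substitute for the withdrawn participant in the analysis.
4. Reconcile this with Section 3.2.1, which classes change or discontinuation of the P2Y12 inhibitor as an anticipated adverse medication effect, and Section 3.2.6, under which registering such an effect leads to withdrawal from the study.

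Decisions on which drugs are given, changed or stopped remain with the care team and are not touched.

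Cost: the remaining scheduled contacts for participants who would otherwise have left, IRB approval of the amendment (Section 6.0), and any matching consent wording. The effect estimate will include non-adherent time and may be somewhat diluted.

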## **2.5.7 Efficiency Assessment**

The efficiency of the study is assessed based on the results of investigational product application, the CYP2C19 genotype-guided preventive treatment with P2Y12 inhibitor and the effectiveness of application of study procedures in real-world clinical practice.

At the 3rd, 6th and 12th months of follow-up, the incidence of the study's primary, secondary and other clinical endpoints (see Chapter 2.6.1 Study Endpoints) will be determined. At the final evaluation, quantitative calculations of their frequency and risk-adjusted clinical outcomes will be performed in the experimental treatment intervention and control arms of the study. Odds Ratio (OR), Relative Risk (RR), Relative Benefit (RB), and Absolute Benefit (AB) indicators will be determined. The efficacy of the study product will be evaluated by considering by evaluation study indicators presented in Appendix 2. Measuring more than three-fourths (>75%) of these indicators will consider the efficiency of the study.

Biases in the study and related evaluations will be avoided by random selection of study participants for intervention and control arms and by excluding confounder variables from the statistical analysis. See study participants' selection procedures in Chapter 2.3.2, Structural Design.

After randomization of the study participants will be allocated into experimental and control arms. 2 experimental arms will be formed based on the results of CYP2C19 genotyping results, one of which will be used as a parallel control group as well. Each arm of the study participants will differ from each other according to the principal characteristic, which is determined by the results of CYP2C19 genotyping, and treatment with a P2Y12 inhibitor will be selected based on the results of CYP2C19 genotyping:

- Clopidogrel treatment in patients with the genotype of CYP2C19 \*2, \*3 normal alleles, "active metabolizers" - experimental arm;
- Clopidogrel treatment without CYP2C19 genotyping, "Unspecified metabolizers group" - experimental arm;
- Clopidogrel alternative P2Y12 inhibitor treatment group, CYP2C19 \*2, \*3 loss-of-function allele genotype, "passive metabolizers" – comparator (control) arm;

Reduction of overlap/confounding of effects will be achieved by homogenized clinical characteristics of experimental and control clinical cases, which will be achieved by strict application of inclusion and exclusion criteria for the selection of all study subjects. This approach equalizes baseline risks and eliminates additional effects due to age, sex, other risk factors and high-risk comorbidities.

The effectiveness of study procedures and possible deviations will be excluded by consistent monitoring and evaluation measures, using the data management system and the validation function of data entry into the electronic database.

